**Table 3. Calculation of Outcome Prevalence**

| Outcome                        | Numerator  | Denominator   |
|--------------------------------|--|---|
| Primary analysis        | Live births and stillbirths with confirmed MCMs ( including MCMs not associated with medication exposure) among individuals with pregnancy outcome data and exposure during the first trimester | Live births among individuals with pregnancy outcome data and exposure during the first trimester |
| Secondary analysis      | Live births and stillbirths with confirmed MCMs ( excluding MCMs not associated with medication exposure) among individuals with pregnancy outcome data and exposure during the first trimester | Live births among individuals with pregnancy outcome data and exposure during the first trimester |
| Minor congenital malformations | Live births with minor congenital malformations among individuals with pregnancy outcome data  | Live births among individuals with pregnancy outcome data   |
| Gestational diabetes           | Gestational diabetes among individuals with pregnancy outcome data   | Individuals with pregnancy outcome data   |
| Preeclampsia                   | Pre-eclampsia among individuals with pregnancy outcome data  | Individuals with pregnancy outcome data   |

| Outcome   | Numerator   | Denominator  |
|--|--|---|
| Fetal loss   | Fetal losses, including SABs, stillbirths, elective or therapeutic abortions, and losses with unknown type, among individuals with pregnancy outcome data                          | Individuals with pregnancy outcome data   |
| SAB  | SABs among individuals with pregnancy outcome data who are enrolled and exposed prior to 20 gestational weeks  | Individuals with pregnancy outcome data who are enrolled and exposed prior to 20 gestational weeks  |
| Stillbirth   | Stillbirths among individuals with pregnancy outcome data  | Live births and stillbirths among individuals with pregnancy outcome data   |
| Elective or therapeutic abortion                                   | Elective or therapeutic abortions among individuals with pregnancy outcome data  | Live births among individuals with pregnancy outcome data   |
| Preterm birth  | Singleton preterm live births without MCMs among individuals with pregnancy outcome data who are enrolled and exposed prior to 37 gestational weeks                                | Singleton live births without MCMs among individuals with pregnancy outcome data who are enrolled and exposed prior to 37 gestational weeks |
| SGA  | Singleton live births without MCMs who are SGA based on weight among individuals with pregnancy outcome data   | Singleton live births without MCMs with weight data among individuals with pregnancy outcome data   |
| Postnatal growth deficiency (at approximately 4 months and 1 year) | Singleton infants without MCMs who were not born preterm, SGA with postnatal growth deficiency based on weight among infants with weight data at the timepoint                     | Singleton infants without MCMs who were not born preterm, SGA with weight data at the timepoint   |
| Infant developmental delay (at approximately 4 months and 1 year)  | Infants without MCMs who were not born preterm with developmental delay in a particular category among infants with developmental milestone data for the category at the timepoint | Infants without MCMs who were not born preterm with developmental milestone data for the category at the timepoint                          |
| Infant hospitalization due to serious illness                      | Infants without MCMs who were not born preterm, with a qualifying hospitalization from birth to 1 year of age among infants with hospitalization data up to 1 year of age          | Infants without MCMs who were not born preterm with hospitalization data up to 1 year of age  |
| Serious or opportunistic infant infection                          | Infants with a qualifying infection from birth to 1 year of age among infants with infection data up to 1 year of age  | Infants with infection data up to 1 year of age   |

MCM = major congenital malformation; SAB = spontaneous abortion; SGA = small for gestational age.

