## 6. DATA COLLECTION

### 6.1. Data Collection Process

Enrolled individuals and the HCPs involved in their care or the care of their infants, if applicable, will serve as data reporters to the surveillance program. If the participant is enrolled by an HCP under an IRB-/EC-approved waiver of informed consent, the HCP who enrolled the participant will be responsible for providing all follow-up data to the surveillance program. It is anticipated that most obstetric data will be collected (directly or via the reporter who enrolled the participant) from the participant's obstetric HCP, defined as any HCP who provides care during pregnancy (e.g., obstetrician, family practitioner, general practitioner); it is anticipated that most pediatric and lactation data will be collected (directly or via the reporter who enrolled the participant) from the infant's pediatric HCP, defined as any HCP who provides pediatric care (e.g., pediatrician, family practitioner, general practitioner). The surveillance program may also request data from other HCPs involved in the individual's or infant's care (e.g., prescriber, specialist) after appropriate medical release is obtained from the individual.

The data collection process for each participant enrolled prior to pregnancy outcome will begin at enrollment, and cumulative data throughout the pregnancy will be collected: at enrollment, at the end of the second trimester (approximately 26 gestational weeks), at pregnancy outcome (live birth or fetal loss), and during lactation. For participants enrolled after pregnancy outcome, all available pregnancy data will be collected at enrollment. For live-born infants, data will be collected at 2 timepoints: approximately 4 months and 1 year after delivery. Data collection forms are described below and will be identical for all enrolled participants regardless of their method of enrollment. Reporters to the surveillance program will use the data collection forms and will be instructed to transcribe data that are readily available in the patients' medical records into the data collection forms. If data are collected via telephone by the VRCC, the VRCC will complete the data collection forms.

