Data related to congenital malformations will be solicited at all data collection timepoints (at enrollment and throughout pregnancy on the **Pregnancy Information Form**, which collects data on prenatal testing, at pregnancy outcome on the **Pregnancy Outcome Form**, and throughout the infant’s first year of life on the **Infant Outcomes Form**). If a congenital malformation (major or minor) or other event of interest is reported, additional information may be requested from the reporter on the **Targeted Follow-up Form** to properly characterize the event. Outcomes of pregnancies that meet serious adverse event (SAE) reporting requirements are included in Section 12.3.2. The date each data collection form is completed will also be collected. Table 1 provides a summary of the data collection process, including the forms that will be used to collect the data, the timing of the completion of each form, the potential reporters or sources of the data, and the types of data that will be collected. Section 6.1.1 provides further details regarding the data collected.

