### **7.3. Participants Lost to Follow-up**

A participant will be considered lost to follow-up if follow-up information is never obtained or is unavailable; pregnant individuals without pregnancy outcome information will be considered lost to follow-up, and live-born infants without follow-up data after birth will be considered lost to follow-up. See Section 6.1.2 for more information on the circumstances under which participants will be considered lost to follow-up. Participants who are lost to follow-up will be excluded from the analysis population, but their demographic and baseline characteristics will be summarized in the reports (see Section 9.2.1).

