Because the surveillance program will enroll individuals only after recognition of pregnancy and in some cases much later in pregnancy, there will be left truncation of the enrolled population. That is, the enrolled population of pregnant individuals will include individuals with a shortened period at risk of the outcomes of interest and will exclude individuals who have already had certain outcomes (e.g., SAB, elective or therapeutic abortion). To minimize the impact of this potential bias, the surveillance program's recruitment strategy will encourage recruitment of participants as early in pregnancy as possible. Since the analysis of surveillance program data is

focused on prospective enrollment, misclassification of drug exposure is non-differential with regard to outcome. However, outcome misclassification could occur especially with regard to minor congenital malformations that may be overlooked or unreported. Although some malformations may not be easily visible at birth, most will be apparent by 1 year of age, so misclassification of these outcomes is expected to be minimal in this surveillance program, which aims to follow infants through 1 year of age.

Pregnancies that result in fetal losses (stillbirths, SABs, and elective or therapeutic abortions) without reported MCMs may introduce a classification bias. The percentage of these pregnancies consisting of potentially normal outcomes or MCMs is unknown. The surveillance program's data collection forms attempt to obtain information on MCMs detected via prenatal testing and at the time of the outcome. However, the reporting physician may not know the condition of the lost fetus.

Finally, it is possible that outcomes among pregnant individuals and infants who are lost to follow-up could differ from those with documented outcomes. Because of differences in individual reporting patterns, it is not possible to assess with any certainty what impact the potential biases from the losses to follow-up may have on the analysis. However, the characteristics of those participants considered lost to follow-up will be descriptively compared with those in the analysis population in an attempt to address this potential source of bias.

The combined impact that potential biases will have on the study results is unknown, but each source of potential bias will be examined and discussed in the reports.

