### **13.5. Study Reports and Publications**

The surveillance program will produce interim study reports annually and a final comprehensive study report at the conclusion of the surveillance program. These reports will be submitted to the appropriate regulatory authorities. Abbreviated interim study reports will include a brief summary of the surveillance program design, methodology, a description of outreach and recruitment efforts, and results to date. The final report will include a comprehensive presentation of the surveillance program design, methodology, and results of the final biostatistical analysis along with an associated interpretive discussion of the surveillance program results. Interim and final reports will include all data received to date, and data will be summarized separately for the analysis population (i.e., prospectively enrolled participants with HCP-confirmed data), retrospectively enrolled participants, and participants with only patient-reported data.

The data may also be considered for reporting at scientific conferences or for publication in scientific journals. Preparation of such manuscripts will be prepared in accordance with the Sponsor's SOPs and the current guidelines of STROBE (STrengthening the Reporting of OBservational studies in Epidemiology) [[STrengthening the Reporting of OBservational Studies in Epidemiology 2009](#)].

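### The primary MCM rate sets no detection cut-off and no infant follow-up condition, so early interim rates mix detection windows and their live-birth part is pulled downward

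*Protocol*

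**What the plan says.** **Numerator and denominator.** In Protocol Table 3 (Section 9.2.2.1) the primary MCM numerator is "Live births and stillbirths with confirmed MCMs", in first-trimester-exposed pregnancies with outcome data. No age limit for detection is given. The denominator is "Live births among individuals with pregnancy outcome data and exposure during the first trimester". The text above Table 3 says that stillbirths count in the numerator but not in the denominator, following the MACDP convention.

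**Ascertainment.** Section 6.1 states: "Data related to congenital malformations will be solicited at all data collection timepoints". These run from enrolment through the first year of life. On timing: "For live-born infants, data will be collected at 2 timepoints: approximately 4 months and 1 year after delivery". Section 9.2.4 says "Although some malformations may not be easily visible at birth, most will be apparent by 1 year of age" and concludes from this that misclassification should be minimal.

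**Inclusion.** Section 7.3 says "live-born infants without follow-up data after birth will be considered lost to follow-up", and then "Participants who are lost to follow-up will be excluded from the analysis population". Section 7.7 instead treats collected pregnancy outcome data as enough not to be lost. The synopsis accepts pregnancy outcome data or infant outcome data.

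**Reporting.** Section 13.5: "Interim and final reports will include all data received to date". Reports are annual and set no minimum infant age.

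**The concern.** The numerator can grow until an infant is 1 year old, but the denominator takes the infant in at birth. At any annual cut, some live births have been assessed at pregnancy outcome only, and others up to about 4 months. Each stands as a non-case for MCMs that would be recognised later. The rate is then neither an at-birth rate nor a 1-year rate, and its mix of windows shifts from report to report.

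Table 3 handles comparable outcomes differently. Growth deficiency and developmental delay require data at the timepoint. Hospitalization and infection require data up to 1 year. The primary outcome, also collected to 1 year, has no such condition.

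What is at stake is the main safety rate, which each report sets beside background rates. A shortfall in its live-birth part leans towards reassurance. The argument in Section 9.2.4 covers only infants who have reached 1 year with data.

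**Working it through.** The protocol states no expected MCM rate, precision or power, so there is no figure to reproduce. The check has three parts.

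**1. Who is in the denominator**

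| Infant at the data cut | Section 7.3 | Section 7.7 / synopsis | Table 3 |
|---|---|---|---|
| Birth data only, 4-month form not yet due | Unclear: lost, or only pending? | In | In |
| Birth data only, forms overdue | Out | In | In |
| 4-month data, no 1-year data | In | In | In |
| 1-year data | In | In | In |

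The first two rows are unsettled. The third is in under every rule, including at the final report.

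**2. Size of the shortfall (live-birth MCMs only)**

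Assumptions, none given in the protocol: uniform accrual, enrolment at 8 gestational weeks, birth at 39 weeks, and a share *s* of MCMs first recognised evenly over the first year, with *s* = 20%, 30% or 50%. From the protocol: infant forms at about 17 and 52 weeks.

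At a cut *T* weeks after start, births come from *T* − 31 weeks of accrual and completed first years from *T* − 83 weeks. The share without a full year is 52/(*T* − 31).

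- *MCMs seen on forms only.* Infants under 17 weeks miss the whole window and older ones miss 35/52 of it: 17 + 35 × 35/52 = 40.6 infant-weeks. Shortfall = *s* × 40.6/(*T* − 31).
- *MCMs between forms fully captured by SAE reporting.* The average unobserved part is one half: 52 × 1/2 = 26. Shortfall = *s* × 26/(*T* − 31).

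| Report year (*T*) | Births without a full year | Forms only, *s* = 20 / 30 / 50% | SAE capture complete, *s* = 20 / 30 / 50% |
|---|---|---|---|
| 2 (104) | 52/73 = 71% | −11.1 / −16.7 / −27.8% | −7.1 / −10.7 / −17.8% |
| 3 (156) | 52/125 = 42% | −6.5 / −9.7 / −16.2% | −4.2 / −6.2 / −10.4% |
| 5 (260) | 52/229 = 23% | −3.5 / −5.3 / −8.9% | −2.3 / −3.4 / −5.7% |
| 10 (520) | 52/489 = 11% | −1.7 / −2.5 / −4.1% | −1.1 / −1.6 / −2.7% |

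If Section 7.3 removes infants under 17 weeks, the forms-only factor at year 2 is (35 × 35/52)/(73 − 17) = 23.6/56 = 0.421. The shortfall is then about −8 / −13 / −21%.

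A simpler model with births uniform from the start gives a ratio to the 1-year rate of 1 − (1 − *a*)/*t*. Here *a* = *q0*/3 + 2*q4*/3, and *q0* and *q4* are the assumed shares known at birth and by 4 months. With *q0* = 0.5 and *q4* = 0.7 the ratio is 82% at year 2 and 96% at year 10. With 0.9 and 0.95 it is 97% and 99%. The pattern is the same.

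**3. Scale against the expected sample**

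Section 9.1 expects 10 to 20 enrolees. Even if all are prospective, first-trimester-exposed and live-born, year 2 has 73/520 × 10 to 20 = 1.4 to 2.8 births. At an assumed true rate of 3% to 10%, the largest shortfall among 2.8 births is 2.8 × 0.278 × 0.03 to 0.10, or about 0.02 to 0.08 of a case. With no MCM observed, the exact 95% upper limit is 1 − 0.025^(1/n): 30.8% for n = 10 and 16.8% for n = 20.

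**The case against.** A reader might infer that every live birth sits in the denominator whatever its follow-up, that unobserved infants are called malformation-free, and that the published rate is therefore biased low. The protocol does not support that much.

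- Section 7.3 removes live-born infants with no data after birth. This stands, but it conflicts with Section 7.7 and the synopsis, and none of them addresses a form that is not yet due.
- Every infant in the denominator was assessed at pregnancy outcome, often after prenatal tests, so only later-recognised MCMs can be missed. This stands.
- MCMs are SAEs (Sections 12.1.2 and 12.3.4), recorded to 1 year after a live birth and forwarded within 24 hours of awareness (Section 12.3.2). This can fill gaps between forms and is why the range above has a lower end. It cannot reveal an MCM before it is recognised.
- Stillbirths in the numerator only push the rate upward, so the net direction is not fixed. This stands.
- The live-birth denominator is a deliberate MACDP convention, missing data will be tabulated (Section 9.2.3), and biases will be discussed (Section 9.2.4). The convention explains the choice of live births but not the absence of a detection window. Nor can this be left to an analysis plan, since Table 3 already fixes the denominator.
- At 10 to 20 enrolees the effect is small beside sampling error. This stands and limits the weight of the point.

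**Conclusion.** The defect is real but modest. As written, the primary MCM rate has no defined detection window, and the rules on which infants belong in it contradict each other. The live-birth part of early interim rates is pulled downward: about 7% to 28% relative at year 2 for 20% to 50% late recognition, depending on how far SAE reporting captures MCMs between forms. At year 10 it is at most about 4%, and that assumes enrolment continues to the final cut. If all follow-up is complete before the final report, it is nil there. These sizes rest on assumed accrual and recognition patterns. They do not establish that the overall rate is too low, and in absolute terms they amount to a small fraction of one case. The point merits a cheap improvement; it does not threaten the study.

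**What to change.** In Table 3, replace the single MCM window with two rates:

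- **(a) At birth:** MCMs recognised by pregnancy outcome, over all first-trimester-exposed live births.
- **(b) By 1 year:** MCMs recognised by 1 year, with numerator and denominator both limited to births whose first birthday plus a stated reporting lag precedes the data cut. Show beside it the number with 1-year data.

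List MCMs in younger infants without a rate. Rate (b) should select on calendar date, not on who returned a form. Keeping earlier-found MCMs while dropping infants without 1-year data would bias it upward: one MCM in 20 births is 5.0%, but 1/16 = 6.2% if only 16 have 1-year data.

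Reconcile Section 7.3, Section 7.7 and the synopsis so that one inclusion rule applies, and say how forms not yet due are treated. Limit the statement on minimal misclassification in Section 9.2.4 to infants with 1-year data.

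Cost: one extra table row and some wording, using dates already collected. Downside: rate (b) rests on very few infants early on, about 21/520 × 10 to 20 = 0.4 to 0.8 at year 2 under the accrual assumed above.

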### **9.2.3. Missing Data**

As described in Section 6.1.2, the surveillance program will make multiple attempts to obtain missing data for critical data points (e.g., exposure and outcome data). The frequency and percentage of participants with missing data for each data point will be presented. Missing data will not be imputed, with 1 exception. For start and end dates of medical conditions or exposures, if month and year are known but day is missing, day will be imputed for analyses; however, listings will continue to present the day as missing. Missing start dates will be set to the first day of the month, and missing end dates will be set to the last day of the month.

### **9.2.4. Limitations of the Research Methods and Statistical Considerations**

The general limitations of pregnancy studies with voluntary participation are well known, and this study will not be an exception. One key limitation of the study is the small size of the population of pregnant or lactating individuals expected to be exposed to omaveloxolone during pregnancy or lactation.

This study is limited by the lack of an appropriate comparator group. Due to the rarity of this disease, the limited number of pregnancies expected among patients, and the high proportion of patients estimated to seek treatment with omaveloxolone, it is not expected that enrollment of an adequately sized untreated comparator group could be achieved in this study. To put the surveillance program data into context, background rates from population-based surveillance systems and the published literature (e.g., MACDP and NVSS) will be referenced in the reports. There are limitations to referencing the study results to risk estimates from a population-based surveillance system, including non-comparable geographic location and distribution (e.g., MACDP is drawn from the metropolitan Atlanta area), non-comparable demographic distributions and genetic composition, and the inability to discern the effects of omaveloxolone exposure from the effects of the underlying disease because comparator risk estimates are calculated in the general mostly healthy population.

Additionally, individuals enrolled in the surveillance program may differ from those in the general population in important factors that could affect pregnancy outcomes. Although it will not be possible to address imbalances (i.e., control for confounding) in the analysis, sources of potential bias will be examined and considered in the interpretation of study results.

Since participation in the surveillance program is voluntary, the individuals who are enrolled in the surveillance program may not be representative of the overall population of individuals who are pregnant or lactating. This could introduce selection bias and affect the generalizability of the results. To minimize the potential for selection bias, a multi-faceted recruitment strategy will be employed, individuals will be enrolled via multiple methods, and data will be collected from multiple sources.

Because the surveillance program will enroll individuals only after recognition of pregnancy and in some cases much later in pregnancy, there will be left truncation of the enrolled population. That is, the enrolled population of pregnant individuals will include individuals with a shortened period at risk of the outcomes of interest and will exclude individuals who have already had certain outcomes (e.g., SAB, elective or therapeutic abortion). To minimize the impact of this potential bias, the surveillance program's recruitment strategy will encourage recruitment of participants as early in pregnancy as possible. Since the analysis of surveillance program data is

focused on prospective enrollment, misclassification of drug exposure is non-differential with regard to outcome. However, outcome misclassification could occur especially with regard to minor congenital malformations that may be overlooked or unreported. Although some malformations may not be easily visible at birth, most will be apparent by 1 year of age, so misclassification of these outcomes is expected to be minimal in this surveillance program, which aims to follow infants through 1 year of age.

Pregnancies that result in fetal losses (stillbirths, SABs, and elective or therapeutic abortions) without reported MCMs may introduce a classification bias. The percentage of these pregnancies consisting of potentially normal outcomes or MCMs is unknown. The surveillance program's data collection forms attempt to obtain information on MCMs detected via prenatal testing and at the time of the outcome. However, the reporting physician may not know the condition of the lost fetus.

Finally, it is possible that outcomes among pregnant individuals and infants who are lost to follow-up could differ from those with documented outcomes. Because of differences in individual reporting patterns, it is not possible to assess with any certainty what impact the potential biases from the losses to follow-up may have on the analysis. However, the characteristics of those participants considered lost to follow-up will be descriptively compared with those in the analysis population in an attempt to address this potential source of bias.

The combined impact that potential biases will have on the study results is unknown, but each source of potential bias will be examined and discussed in the reports.

